6.9.3 Neutropenia

Hematological assessments will be performed as previously described. If Absolute Neutrophil Counts \leq 1000 cells/ μ l are documented, treatment should be discontinued, and CBC will be repeated as soon as possible after the initial abnormality is identified. After that, the participant should be followed every 48 hours (2 days), or the closest possible interval, until the neutrophil counts increase above 1000 cells/mm or stabilize. The event should be immediately reported as an SAE.

In case Absolute Neutrophil Count is found to be $<$ 500 cells/ μ l, the treatment should be immediately interrupted, and a control hematological assessment is required within one day. Participants will be instructed to avoid exposure to people with respiratory tract infections and to respect general hygiene rules. Depending on profile (decreasing phase, stabilization phase, resolution phase), controls will be required every one to three days until normalization. The event should be immediately reported as an SAE.

In case Absolute Neutrophil Count is found to be $<$ 100 cells/ μ l, or below 1000 with associated fever (even of mild intensity) or infectious origin symptoms, the participant should immediately be hospitalized and reported as an SAE.

7. Laboratory assessment

Blood samples for hemogram and biochemistry (5mL each) will be collected in the same day at screening, at days 14 (allowable window of + 2 days), and 56 (allowable window of + 7 days).

Blood samples for serology will be collected at screening visit and at month 24 after EOT.

Blood samples for PCR will be collected at screening visit and at 1, 4, 6, 8, 12, 18 and 24 months after EOT (allowable window of + 10 days. Blood samples collected for PCR shall be immediately added to a tube containing one volume (5mL) of a solution of Guanidine/ClH 6M EDTA 0.2M pH 8,0 Buffer (GEB). Samples

with guanidine buffer can remain at room temperature. Trained nurses will be responsible for the blood collection, sample processing and storage.

The PCR technique that will be used is the one described by Duffy et al. (29) and optimized by the Molecular Biology Institute of Paraná (IBMP). That procedure allows the amplification of a *T.cruzi* satellite DNA region and a linearized recombinant plasmid used as an internal amplification control. The PCR will be carried out in duplicate from each of three extractions. At least one amplification of the six performed with an amplification cycle (C_t) of *T.cruzi* below 40 and a correct value of internal amplification control will be interpreted as positive. To assess the homogeneity of the results obtained by the different laboratories, a harmonization panel will be constituted and sent to the laboratories.

Back-up samples for serology and PCR will be stored in each laboratory as for quality and warranty purposes.

The study manual of operations will provide full details regarding procedures for sampling (tube types and amount, aliquots volume), handling, storage, and shipment of the samples for laboratory evaluation. Quality assurance systems will be in place and described. Training of personnel in each of the activities described above will take place before initiation of this clinical trial. All parasitological and other laboratory assessments will be performed blinded to treatment allocation.

7.1 Governance of biological specimens

The study will be performed in two different countries, Bolivia and Colombia. After consulting the regulatory agencies of each country, it has been confirmed that there is no minimum time required for sample storage. The storage period for human biological material in a Biorepository must be in accordance with the corresponding research schedule with a maximum for up to ten years. By consensus, we have decided to store samples for up to 5 years after completion of the study.

Samples will be stored at national reference laboratories previously identified in each country:

- Colombia: Instituto Nacional de Salud, [name].
 - Responsible for sample custody: [name] and [name].
- Bolivia: Instituto Nacional de Laboratorios de Salud (INLASA). [name].
 - Responsible for sample custody: [name]

The objective of storing samples is part of good clinical practice commitments, in case we need to repeat or confirm any result. If another research needs to use stored samples, it will be submitted for approval by the Research Ethics Committee and patients will be asked to reconsent. Although the final responsibility over samples lies with the sponsor, Oswaldo Cruz Foundation (Fiocruz), a democratic mechanism for decision-making will be established, considering all the opinions of the country Principal Investigators.

In the case that samples need to be destroyed, a certified enterprise will be contracted.

8. Scheduled Visits

As described previously, study assessments will be done at Screening, Day 0 (baseline), at 2 weeks (allowable window of ± 2 days), 4 weeks (allowable window of ± 2 days), and 8 weeks (allowable window of ± 7 days). Afterwards, assessments will be done every 6 months (allowable window of ± 14 days) until the end of study (24 months).

Patients will have a total of 5 visits between the inclusion and the treatment period, each visit lasting approximately 2 hours. Afterwards, there will be 7 additional visits which will be shorter, lasting approximately 1 hour each. The per protocol participation will take 26 months of follow up.

8.1 Screening visit

The centers chosen to participate in the study are already considered reference centers for the treatment of Chagas disease. Each center has its own patient referral flows framed within each health system. The doctors who treat the patients themselves who will offer them the possibility of participating in the clinical trial as long as they meet all the inclusion criteria and none of the exclusion criteria.

During screening, the following assessments will be done to evaluate participant eligibility for the study:

- Signature after reading the Informed Consent Form;
- Complete medical history with an emphasis on CD;
- Demographic data, history of medications and toxic habits;
- Physical examination, body weight/height and vital signs;
- CD serology: serum sample will be documented at screening for conventional CD serology. Participant must have at least 2 positive tests to be eligible;
- Real-time PCR collected for quantitative assessment for all participants (result is not required for randomization);
- Clinical safety laboratory evaluations (whole blood and serum sample): hemoglobin, total white blood cells (WBC) count, differential WBC count, numerical platelet count, ALT, AST, urea, creatinine;
- Serum pregnancy test: women of reproductive age will undergo a serum pregnancy test at screening. The test must be negative for the woman to be considered eligible for this study;
- EKG: will be obtained at screening. Participants with abnormal EKGs will undergo an echocardiogram.

8.2 Baseline visit

At baseline (Day 0) the following assessments will be performed before the first dose of medication is administered, to obtain baseline safety data and data for further comparative analyses and multiple parameter correlations:

- Physical examination (including weight);
- Vital signs: axillary temperature, blood pressure and pulse rate;
- WHOQOL Bref, EQ-5D-3L and cost-effectiveness questionnaires will be distributed and will be completed by the participant (See Annexes 1, 2 and 3, respectively).

Concomitant medications at baseline will be recorded in the appropriate CRF.

The participant's eligibility criteria evaluation will be performed at day 0, or when the investigator has access to all results necessary for the participant's inclusion/exclusion evaluation. After participant eligibility is confirmed, randomization will occur, and the participant will receive the first kit of medication at the clinic.

8.3 Treatment visit

Three regular visits will be required during the treatment period, at 2, 4 and 8 weeks after the start of treatment. During each visit, the participant will be asked about the appearance of AE. If the researcher considers that such signs and symptoms are related to the drug (BZN), all measures that the researcher deems necessary will be carried out. Each case will be assessed individually and depending on severity and causality, treatment may be withdrawn definitively, suspended momentarily or concomitant medication may be administered.

- Visit at 2 weeks (+/- 2 days): Directed anamnesis and physical examination. Analytical extraction (hematology, biochemistry. Evaluation of AE and changes in concomitant medication. At this visit, the 1st kit of medications (BZN or placebo) will be collected, and the 2nd kit will be distributed to the participant.
- Visit at 4 weeks (+/- 2 days): Directed anamnesis and physical examination. Evaluation of AE and changes in concomitant medication. At this visit, the 2nd kit of medications (BZN or placebo) will be collected, and the 3rd kit will be distributed to the participant.
- Visit at 8 weeks (+/- 7 days): Directed anamnesis and physical examination. Extraction of laboratory tests (hematology, biochemistry. Evaluation of AE and changes in concomitant medication. In this visit the 3rd kit of medications (BZN or placebo) will be collected.

EQ-5D-3L and cost-effectiveness questionnaires will be distributed to and completed by the participant during each visit.

8.4 Adverse event management

During the treatment phase, participants should seek medical consultation in the event of any AE. The participant then will undergo directed anamnesis and physical examination. The clinical need for analytical extraction will be considered (hematology and biochemistry). AE will be evaluated, as well as potential changes in concomitant medication.

The criteria for withdrawal of the medication will be decided by the doctor treating the participant, considering the severity, intensity and extent of the AE. In addition, a participant may decide to suspend medication at any time during the treatment or upon the appearance of any AE.

If an AE occurs and the opinion of the investigator advises the interruption of treatment, the medication will be suspended, and symptomatic treatment will be instituted following the scheme defined in section

6.9 or at medical discretion. The participant may present different AE during the treatment phase that require treatment interruption. The duration of the study medication interruptions will depend on each AE and will be done at the discretion of the doctor treating the participant. If the drug suspension exceeds 15 days, the study medication will be permanently withdrawn from the participant. If finally, it is decided to definitively withdraw the drug due to an AE, the participant will be recalled 14 days later and will be questioned again about the possibility of late AE. Should the participant not be able to make a visit, a phone call will be accepted, which must be recorded in the source document.

8.5 Follow up visit

During the follow-up phase, visits will be made every six months, regardless of the assigned study branch. At each visit, the following will be carried out: directed anamnesis, physical examination, EKG and determination of the parasitic DNA by PCR. Depending on evolutionary electrocardiographic changes and availability, an echocardiogram may also be requested. The times of visits will be in month 1, 4, 6, 8, 12 and 18 after the end of treatment (with a window of +/- 10 days).

EQ-5D-3L and cost-effectiveness questionnaires will be distributed to and completed by the participant during each visit.

8.6 End of study visit

At the end of the follow-up of each participant, coinciding with month 24 (+/- 15 days) after the end of treatment, a directed anamnesis, physical examination, EKG, determination of the parasite DNA by PCR and serology will be performed and changes in concomitant medication will be recorded. Depending on evolutionary electrocardiographic changes and availability, an echocardiogram may also be requested. WHOQOL BREF and EQ-5D-3L questionnaires will be distributed to and completed by the participant.

9. Pharmacovigilance

9.1 Adverse event definition

AE is defined as any unexpected medical occurrence in a participant or clinical trial participant after the administration of a pharmaceutical product and which does not necessarily have a causal relationship with the treatment. AE include worsening (in severity and frequency) of pre-existing conditions ("Medical history") before the first Investigational Medicinal Product (IMP) administration and abnormalities of procedures (e.g. EKG) or laboratory results which are assessed as "clinically significant".

Laboratory / procedure abnormalities considered as AE

Laboratory / procedure abnormalities (or worsening in severity or frequency of pre-existing abnormalities)

assessed as “clinically significant” must be reported as an AE only if they meet at least one of the following conditions:

- The abnormality suggests a disease and/or organ toxicity AND this abnormality was not present at the screening visit or is assessed as having evolved since the screening visit;
- The abnormality results in discontinuation of the study drug;
- The abnormality requires medical intervention or concomitant therapy.

When reporting an abnormal laboratory/procedure result, a clinical diagnosis should be recorded rather than the abnormal value itself (for example, “anemia” rather than “decreased red blood cell count”).

What is not an AE?

- Medical conditions present at the initial study visit that do not worsen in severity or frequency during the study are NOT considered as AE;
- Symptoms, exacerbation or worsening of the studied disease will NOT to be considered as AE nor captured on the AE page of the CRF if consistent with the anticipated natural progression of the disease (overall and for this given participant);
- Lack of efficacy of the investigational product is NOT considered as AE.

The investigator or appropriate site personnel will examine any participant experiencing an AE as soon as possible. The investigator will do whatever is medically necessary for the safety and well-being of the participant.

The participant will remain under observation as long as a participant is receiving trial drug, and for two months following the last day of drug administration, or longer if medically indicated in the opinion of the investigator. All AEs observed or reported following administration of IMP will be followed until resolved or until medically stable. All AE identified will be assessed for seriousness, severity, and causality and recorded in the appropriate AE section of the CRF using standard medical terminology to avoid the use of vague, ambiguous, or colloquial expressions.

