2.1 Treatment toxicity

The main drawback of BZN and NFX is their high adverse event ratio. The frequency of adverse effects with NFX ranges from 43.0 to 97.5% with the most common being anorexia, weight loss, neurological disorders (irritability, insomnia, disorientation, mood changes, paresthesia, and peripheral neuropathy), digestive manifestations such as nausea and vomiting, and, occasionally, fever and rash. Treatment is discontinued in 14.5–75.0% of cases. (24) For BZN, the most common adverse effects involve hypersensitivity, mainly in the form of skin rash (29–50%), digestive intolerance (5–15%), and general symptoms such as anorexia, asthenia, headache, and sleeping disorders (40%). Neuropathy and depression of bone marrow are considered rare. Treatment is discontinued in 9–29% of cases, even though most reactions are reversible, and severe cases occur in less than 1%. BZN is generally preferred over NFX because of its better tolerability profile. (18)

Since the major limitation of nitroderivative-based therapy is its toxicity, which hampers its efficacy and adherence rates, different approaches have been designed to improve tolerance, mainly based on overall dose reduction. (25)

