The main objective of the MULTIBENZ clinical trial was to evaluate the efficacy of different BZN regimens at 12 months post-initiation of treatment in patients with CD in the chronic phase. The primary efficacy outcome was defined as the proportion of patients with suppression of sustained parasitic load in peripheral blood measured by polymerase chain reaction (PCR) during the first 12 months of follow-up after randomization.

Patients were randomly assigned to receive BZN 150 mg/day for 60 days, 400 mg/day for 15 days, or the

standard regimen (300mg/day for 60 days). The total number of patients who were estimated to be included in the study was 240, 60 participants per country and 80 per treatment arm.

The preliminary efficacy analysis of the study (not yet published) did not demonstrate statistically significant differences between the therapeutic regimens evaluated in Bolivia, Argentina, and Colombia. However, patients treated for 15 days had 10% of treatment failure compared with 5% of those receiving the standard regimen (although they did not reach statistical significance).

Therefore, taking into account the results of the MULTIBENZ and BENDITA studies, where different therapeutic regimens have been evaluated, we consider that both the options of Benznidazole 300 mg per day for 2 or 4 weeks, are equally valid to be evaluated in a phase III clinical trial compared to the standard dose of Benznidazole of 300 mg per day for 8 weeks.

3. Objectives and Endpoints

Objectives	Endpoints
Primary	

 To compare the efficacy of BZN in two reduced treatment schemes with a fixed oral dose of 300mg/day for 2 weeks or 300mg/day for 4 weeks compared to the standard treatment of 300mg/day for 8 weeks in the treatment of chronic CD, in its indeterminate or mild cardiac forms. 	
 Proportion of participants with sustained negative PCR at 24 months of follow-up after treatment.
Secondary	

 To evaluate the safety profile of a fixed oral dose of 300mg/day for 2 weeks or 300mg/day for 4 weeks compared to the standard treatment of 300mg/day for 8 weeks in the treatment of chronic CD, in its indeterminate or mild cardiac forms. 	
 Incidence of AE leading to treatment discontinuation.

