6.9.1 Hypersensitivity reactions

In the event of a hypersensitivity related AE depending on the severity, the following symptomatic treatment regimen will be followed, at the investigator's discretion:

- Mild AE: cetirizine 10 mg every 24 hours orally (or other similar antihistamine drug).
- Moderate AE: cetirizine 10mg every 12 hours or +/- prednisone 0.5 mg/kg every 24 hours orally.
- Serious AE: cetirizine 10 mg every 8 hours or +/- prednisone 1mg/kg mg every 24 hours orally. Indication of hospitalization will be assessed.

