9.2 Serious adverse event

An SAE is any unexpected medical occurrence that:

- Results in death;
- Is life-threatening, i.e in this context refers to an AE in which the participant was at risk of death at the time of the AE; it does not refer to an AE that hypothetically might have caused death if more severe;
- Results in persistent or significant disability or incapacity, i.e. the AE resulted in a substantial disruption of the participant’s ability to conduct normal activities;
- Requires in-patient hospitalization or prolongation of existing hospitalization (note: this clinical trial does not have any period of scheduled hospitalization), i.e. the AE requires at least an overnight admission or prolongs a hospitalization beyond the expected length of stay. Hospital admissions for surgery planned before study entry, for social reasons, for any elective surgery (i.e. plastic surgery) or for normal disease management (including treatment adjustment) are not to

be considered as SAE according to this criterion (i.e. if the protocol or the standard management of the disease under study requires planned hospitalization);

- Congenital anomaly/birth defect, i.e. an AE outcome in a child or fetus of a participant exposed to the IMP (or marketed medicinal product (Note: only to be added for marketed drug)) before conception or during pregnancy;
- Important medical event, i.e. is medically significant. Medical and scientific judgment should be exercised in deciding whether other situations should be considered serious events/reactions, such as important medical events that might not be immediately life-threatening or result in death or hospitalization but might jeopardize the participant or might require intervention to prevent one of the other outcomes listed above. Examples of such medical events include allergic bronchospasm requiring intensive treatment in an emergency room or at home, blood dyscrasias or convulsions that do not result in in-patient hospitalization, or the development of drug dependency or drug abuse.

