9.7 Grading of Adverse Event severity

Severity is a clinical determination of the intensity of an AE. The severity for an AE should be graded using the National Cancer Institute's Common Terminology Criteria for Adverse Events (CTCAE, version 5.0)⁵, defining the System Organ Class (using preferred terms defined by MedDRA 13.1). In case of AEs that are not described in the CTCAE v5.0, the investigator will use the terminology MILD, MODERATE, or SEVERE to describe the maximum severity of the AE as follows:

- **MILD** Does not interfere with the patient's usual functions;
- **MODERATE** Interferes to some extent with the patient's usual functions;
- **SEVERE** Interferes significantly with the patient's usual functions.

This information on AE grading will be entered in the AE section of the CRF. It is to be noted the distinction between severity and seriousness of AE. An SAE is not necessarily a serious event.

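### Protocol 9.1 and 9.2 define AEs and SAEs as unexpected events, which read literally leaves out known clinical benznidazole reactions; separately, 9.7 confuses severe with serious

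*Protocol*

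**What the plan says.** Protocol 9.1: "AE is defined as any unexpected medical occurrence in a participant or clinical trial participant after the administration of a pharmaceutical product". No causal link to treatment is required. Protocol 9.2 begins: "An SAE is any unexpected medical occurrence that", followed by the seriousness criteria. Neither section says what *unexpected* means or against which reference it is judged.

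Protocol 9.7 announces a contrast, "It is to be noted the distinction between severity and seriousness of AE", and the next sentence reads "An SAE is not necessarily a serious event".

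Protocol 6.9.1 sets out three tiers of hypersensitivity reaction. The first two are labelled mild and moderate; the third begins "Serious AE: cetirizine 10 mg every 8 hours". The general text of 6.9 and the scale in 9.7 both use mild, moderate and severe.

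The secondary safety endpoint in Section 3 is "Incidence of AE leading to treatment discontinuation".

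**The concern.** Expectedness describes what is already known about a drug. It is useful as a separate attribute of an event, but it does not decide whether an event happened or whether it met a seriousness criterion. Here it stands inside both definitions as a condition of entry.

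The drug's common reactions are known in advance. Section 2.1 gives rash at 29–50%, digestive intolerance at 5–15% and general symptoms at 40%. A site that applied 9.1 to the letter would not record a typical rash as an AE. If such a rash led to admission, the opening words of 9.2 would keep it from being an SAE.

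Two things depend on these definitions. One is the safety comparison, which counts AEs leading to discontinuation and is the trial's superiority question. The other is safety oversight, because under 9.6 the serious or non-serious classification decides the reporting route, including the 24-hour report. Section 9.3 names no AE of special interest, on the ground that the drug is well known, so no second list catches a known reaction that the definition drops.

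The sentence in 9.7 is a different fault. It blurs the term that decides the reporting route.

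**Working it through.** The point rests on definitions and the plan states no figure for it, so the check sets the sections side by side.

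**1. What the opening sentences exclude.** Known clinical reactions (2.1) are rash and other hypersensitivity, digestive intolerance, and general symptoms such as anorexia, asthenia and headache. Being known, they are not unexpected in the ordinary sense of the word, and the protocol offers no other sense.

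**2. What remains covered in any case.** Section 9.1 has its own list for laboratory and procedure abnormalities. Clinically significant ones count as AEs if, for example, they lead to discontinuation of the study drug, and that list does not ask whether they were expected. Section 6.9.3 requires neutropenia to be reported as an SAE. The literal gap therefore concerns clinical reactions, not every known toxicity.

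**3. Where the protocol treats known reactions as AEs or SAEs.**
- 6.9.1 calls hypersensitivity reactions AEs and grades them.
- 6.9.3 makes neutropenia an SAE, although 2.1 names bone-marrow depression as a known (rare) effect.
- 9.2 itself gives allergic bronchospasm and blood dyscrasias as examples of important medical events. Both belong to reaction types named in 2.1.
- 10.3 expects 20% of control participants to be withdrawn because of any AE, and 10.1 plans on 20% interruption with a 50% reduction, that is 20% × (1 − 0.50) = 10%. A 20% rate on a well-known drug presupposes that known reactions count.

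Steps 1 and 3 cannot both be followed as written.

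**4. Whether another section cures the conflict.** Section 9.4 requires all observed and spontaneously reported AEs, with a checklist interview at each visit. Section 9.5 requires treatment-related AEs in the CRF. Both use the term AE, whose content 9.1 sets, so neither enlarges it.

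**5. Section 9.7 against 9.2.** Under 9.2 an event is an SAE because it meets a seriousness criterion, so an SAE is serious by definition. The sentence in 9.7 denies this. The sentence before it concerns severity versus seriousness, so the intended statement must be that a severe event need not be serious. This error stands alone: it puts no reaction inside or outside the AE definition.

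**6. Size.** The documents give no share of events that would go unrecorded. Purely as an illustration, assume that a share *s* of discontinuation AEs is missed equally in both arms. With n = 224 per arm and two-sided 0.05, the rates are p₁ = 0.20(1 − s) and p₂ = 0.10(1 − s), p̄ is their mean, and

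power = Φ{[(p₁ − p₂)√n − 1.96√(2p̄(1 − p̄))] / √(p₁(1 − p₁) + p₂(1 − p₂))}

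- s = 0 (20% v 10%): about 84%
- s = 0.25 (15% v 7.5%): about 71%
- s = 0.50 (10% v 5%): about 52%
- s = 0.75 (5% v 2.5%): about 28%

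The values of *s* are assumptions with no source in the protocol. The list shows only the direction of the effect if capture failed. It does not estimate the harm.

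**The case against.** The strongest reply is that the protocol, read as a whole, shows that known reactions count. The word *unexpected* is never tied to a label or a list of known reactions. Section 9.1 lists what is not an AE, and known drug reactions are not on that list. Sections 6.9.1, 6.9.3, 9.2, 9.4, 9.5 and 10.3 all point the same way, and most investigators would record a rash. This stands as evidence of intent and limits the practical harm. It does not repair the definitions, because the sections that show the intent contradict them and the collection rules borrow their key term from 9.1.

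A reader might infer more than the documents support, in four ways:
- *That the safety endpoint omits known reactions.* The evident intent is against this. What is present is a contradiction that sites could resolve differently.
- *That rash, digestive intolerance and general symptoms make up most of the planned 20% v 10% contrast.* Section 2.1 says how often these reactions occur and gives an overall discontinuation range of 9–29%. It does not split discontinuations by cause, and 10.1 and 10.3 do not either.
- *That the SAE table in 10.9 will be distorted.* SAE status follows the criteria in 9.2. Section 9.1 has seriousness and severity assessed separately, and 9.6 has each AE classified as serious or not. The slip in 9.7 and the label in 6.9.1 may confuse, but distortion is not shown.
- *That the third tier in 6.9.1 should be relabelled as severe.* The tiers govern symptomatic treatment, so the choice of label could affect who enters a tier. A statistical review can only ask that the passages be reconciled.

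**Conclusion.** The point holds as an internal contradiction in operative text. The opening sentences of 9.1 and 9.2 literally leave out known clinical benznidazole reactions, while 6.9.1, 6.9.3, the examples in 9.2 and the planning rate in 10.3 include them. The consequence is a risk of inconsistent capture of AEs leading to discontinuation, which Section 3 lists as a secondary endpoint, and of SAEs. The documents do not allow that risk to be quantified. This rests on taking *unexpected* in its ordinary sense, since the protocol defines no other. The sentence in 9.7 is a second, independent error that contradicts 9.2 on its face, and the third-tier label in 6.9.1 does not match the terms in 6.9 and 9.7. The correction is worth making because these definitions feed both the safety endpoint and expedited reporting, and changing them costs almost nothing.

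**What to change.** - In 9.1 and 9.2, replace *unexpected* with *untoward, whether or not expected*. Keep expectedness as a separate attribute of the event.
- In 9.7, replace the faulty sentence with *A severe AE is not necessarily a serious AE*.
- Ask the sponsor to reconcile the third-tier label in 6.9.1 with the mild, moderate and severe terms in 6.9 and 9.7, without changing any treatment rule.

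The cost is these wording edits, handled through the protocol's amendment procedure, and a short note to sites so that all of them record known reactions in the same way. Visits, sample size and analyses do not change.
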